5.2.9 Optional Quit Smoking Session (1-2 weeks following study completion)

After completing Scan 2, participants will be given the opportunity to obtain additional quit resources. Participants may opt to attend an in-person session or complete a call with one of our trained quit smoking counselors. During the call or in-person session there will be a discussion of reasons for quitting, the model of smoking as a learned habit, triggers for smoking, and trigger management. Participants will receive brief training in how to manage withdrawal symptoms and relapse prevention counseling (e.g., identifying high risk situations or triggers to smoke, being prepared for and coping with high risk situations, limiting access to cigarettes, managing a slip and preventing a relapse, developing a personal relapse prevention plan, and managing a complete relapse). Smokers will also receive the NCI Clearing the Air self-help smoking cessation booklet. This session is completely optional and is for the sole purpose of providing participants who are interested in quitting an opportunity to gain helpful tools to aid them in potential quit attempts. There is no data collection or compensation associated with this session.

5.2.10 1-Month Follow-up Survey

Smokers who complete all study in-person study visits will be contacted at minimum 4 weeks after their last study visit (Period 2 Session 4) by phone to complete a brief survey of their smoking and eating behaviors. Participants will complete the Smoking Related Eating and Episodes Test (SWEET)*** and two questions relating to readiness and intention to quit smoking in addition previously collected questions about withdrawal symptoms (MNWS)***, Positive and Negative Affect (PANAS)***, and smoking urges/craving (QSU-B)***. Participants who are classified as study completers as of 4/14/2020 (N = 15) will be re-contacted by phone to completed re-consent before the survey administration.

CONFIDENTIAL

This material is the property of the University of Pennsylvania. Do not disclose or use except as authorized in writing by the study sponsor

Table 2. Study Measures and Time Points

Days	Phone Screen	Intake -14	Baseline -7	Period 1				Wash-out 5-28	Period 2				De-brief Call ~32	Follow-up ~59
	-15			1	2	3	4		29	30	31	32		
SCREENING/COVARIATES														
Urine Drug Screen		x	x				x					x		
Urine Pregnancy Screen (if applicable)		x					x					x		
Breath Alcohol (BrAC)		x	x				x					x		
Height		x												
Weight		x	x	x			x		x			x		
Medical History Form***		x												
fMRI Medical Hx. Form***		x												
Magnet Safety Form***		x					x					x		
Emergency Contact Form***		x												
Demographics***		x												
ETOH History***		x												
Smoking History/Nicotine Dependence (FTND)***		x*												
Smoking Rate (TLFB)			x*	x*	x*	x*	x*		x*	x*	x*	x*		
Cigarette Brand Form***		x*												
Shipley Institute of Living Scale (SILS)***		x												
Carbon Monoxide (CO)		x	x*	x*	x*	x*	x*		x*	x*	x*	x*		
Eating Behavior (DEBQ)***			x				x					x		
Eating Inventory-Disinhibition (EI-D)***				x			x					x		
Depression Symptoms (CES-D)***				x										
Smoking Urges/Craving (QSU-B)***			x	x*	x*	x*	x*		x*	x*	x*	x*		x
Weight Concerns***			x											
Debriefing Phone Call													x	
MECHANISMS														
Working Memory			x				x* *					x**		
Food Reward			x											
Preferred Snack Choice (Pre-RRVF)			x											
Food Reinforcement (RRVF)							x* *					x**		
Pre-FCQ-S			x											

CONFIDENTIAL

This material is the property of the University of Pennsylvania. Do not disclose or use except as authorized in writing by the study sponsor

Food Cue-Induced Craving (FCQ-S)							x*					x**		
Withdrawal Symptoms (MNWS)* ***			x	x	x	x			x	x	x	x		x
Positive and Negative Affect Schedule (PANAS)***			x	x	x	x			x	x	x	x		x
Readiness/Intention to Quit Smoking***														x
Smoking-Related Eating and Episodes test (SWEET)***														x
PRIMARY OUTCOMES														
Caloric Intake (Dietary Recalls)				x	x	x			x	x	x			
% Eligible at Intake (pilot)	x													
SECONDARY OUTCOMES														
Attitudes towards research (pilot)	x													

*Smokers only

**Assessed in fMRI

***Denotes measures that can and will be collected remotely using REDcap.

5.4 Description of Study Measures

Similar to Section 5.2 In-Center Study Visits and Table 2 above, measures that can be collected remotely using REDcap are denoted with three asterisks (***)�

5.3.1 Screening/Covariates

Urine Drug Screen: A urine sample (~30ml) will be collected at the Intake Visit and both neuroimaging scans to conduct a urine drug screen. The urine drug screen indicates whether the subject has recently taken any of the following recreational drugs or medications: THC, cocaine, opiates, amphetamines, methamphetamines, phencyclidine (PCP), ecstasy (MDMA), barbiturates, benzodiazepines, methadone, tricyclic antidepressants, and/or oxycodone. Participants with a positive urine drug screen for any substance listed above other than THC or tricyclic antidepressants at the Intake visit will be deemed ineligible. A urine sample that doesn't register a temperature reading of at least 90 degrees Fahrenheit will not be considered a valid sample. In an effort to remain CLIA-compliant, results from urine drug screen will not be shared with participants. Participants will be informed that the testing is for research purposes only and that they will be informed of their eligibility status, but not of the specific testing results. In order to document inclusion/exclusion criteria for regulatory purposes, results of the urine drug screens (test cup) will be retained in research charts and in an electronic research record within our local data management system (Access). These results are not and will not be entered into a participant's electronic medical record.

Participants who test positive for any study-prohibited medications/recreational drugs at either neuroimaging scan will be deemed ineligible.

Urine Pregnancy Test: At the Intake Visit and both neuroimaging scans, female participants will be supplied with a simple, CLIA-waived hCG pregnancy test strip and a urine sample cup

CONFIDENTIAL

This material is the property of the University of Pennsylvania. Do not disclose or use except as authorized in writing by the study sponsor

(participants may use the urine drug screen cup if desired). Participants will then be instructed to self-administer the pregnancy test and be told that if they are (or believe they may be) pregnant they should not participate in the research study. The participants will inform the study staff if they are able to continue participation after they have reviewed the results of the pregnancy test. Participants will be informed that there is no penalty for discontinuing participation at this point in the visit and that they will still be provided their preferred travel coverage for the visit.

Breath Alcohol Concentration (BrAC): Participants will complete a BrAC assessment at the Intake Visit and both neuroimaging scans. Participants will be made aware of the BrAC assessment prior to all applicable visits and asked to avoid alcohol and alcohol-based products (e.g. mouthwash, breath spray, etc.) the evening and morning before the Intake Visit and both neuroimaging scans. The BrAC monitor is a handheld device that uses a disposable mouthpiece and reports the concentration of alcohol in exhaled breath. Any reading greater than 0.000 indicates alcohol consumption within the last 14 hours. Participants with a BrAC greater than 0.000 at the Intake Visit will be deemed ineligible. Participants with a BrAC greater than 0.000 at either neuroimaging scan will be deemed ineligible unless the Principal Investigator permits the participant to reschedule the neuroimaging scan to another day.

Height: Research staff will collect and document participant height utilizing a mounted stadiometer at the Intake Visit.

Weight: Weight will be measured by a physician's scale (pounds) at the intake visit. Participants will be wearing light clothing without shoes. Participants weighing over 275 pounds at intake will be deemed ineligible.

Medical History Form***: A medical history form (led by the research staff) will be completed to review for applicable contraindications previously listed under Key Inclusion/Exclusion Criteria at the Intake Visit.

fMRI Medical History Form***: Participants who met the initial fMRI eligibility criteria at phone screen will be asked to complete a separate fMRI medical history form to review for applicable contraindications previously listed under Key Inclusion/Exclusion Criteria.

Magnet Safety Form***: Participants will complete a standard magnet safety form provided by the Department of Radiology at the Hospital of the University of Pennsylvania at the Intake visit and before entering the scanner at each fMRI scan. The magnet safety form assesses a history of specific prosthesis, surgical implants, and a variety of other MRI contraindications.

Emergency Contact Form***: Participants will provide emergency contact information in the event of an emergency at the fMRI scanner.

Demographics, Smoking History, Cigarette Brand, and Nicotine Dependence (FTND)***: Standard questionnaires will be administered at the Intake Visit to collect the following data: demographics, age at smoking initiation, current smoking rate, previous quit attempts, and own cigarette brand information (Cigarette Brand Form). The Fagerstrom Test for Nicotine Dependence (FTND) will also be administered. The FTND is a 6-item, self-report measure of nicotine dependence derived from the Fagerstrom Tolerance Questionnaire. The FTND scale has satisfactory internal consistency (Cronbach's alpha = .64) and high test-retest reliability ($r=.88$).

Smoking Rate Timeline Follow Back (TLFB): A reliable and valid timeline follow-back method will be used to assess daily smoking (presence and rate) at every visit post Intake.

CONFIDENTIAL

This material is the property of the University of Pennsylvania. Do not disclose or use except as authorized in writing by the study sponsor

ETOH History***: An ETOH history questionnaire will be administered at the Intake Visit and will assess alcohol consumption over the past 7 days.

Shipley Institute of Living Scale (SILS)***: All participants will complete the SILS at the Intake Visit. The SILS is a self-administered test designed to assess general intellectual functioning in adults and adolescents and to aid in identifying cognitive impairments. The scale consists of two subtests: a 40-item vocabulary test and a 20-item test of abstract thinking. The total administration time is 20 minutes (10 minutes per subtest). A trained member of the study staff will score the test. The SILS correlates with the Wechsler Adult Intelligence Scale-Revised (WAIS-R) Estimated IQ Test; those participants earning less than an estimated WAIS-R IQ of 85 will be ineligible. The SILS is considered a highly reliable assessment tool with good total score internal consistency (Cronbach's alpha= .92).

Hunger Scale***: Immediately prior to and after completion of computerized laboratory tasks, participants will be asked to rate, "How hungry are you right now?" using a scale from 0 "not at all" to 10 "extremely."

Eating Behavior (DEBQ)***: The Dutch Eating Behavior Questionnaire will assess restrained eating (10 items, tendency to restrict food intake), external eating (10 items, tendency to eat in response to food related cues) and emotional eating (13 items, tendency to eat in response to emotions). These scales are associated with food craving and response to food cues. Participants indicate on a Likert-style scale how often each item is applicable to them (0= not relevant; 1 = never to 5=very often).

Eating Inventory-Disinhibition (EI-D)***: Disinhibition will be measured with a subscale (16 items) of the Eating Inventory that is thought to reflect responsivity to environmental food cues, and internal cues, and linked to food reinforcement and weight change.

Carbon Monoxide (CO): CO will be measured at the Intake Visit for all participants and at all subsequent in-person visits to confirm smoking status of the smoking group. The CO monitor is a handheld device that uses a disposable mouthpiece, reports CO in parts per million (ppm), and takes about 3-5 minutes to administer.

Depression Symptoms (CES-D)***: The Center for Epidemiologic Studies Depression Scale is a 20-item Likert-style scale used to assess depressive symptomatology. This scale has high internal consistency ($r=.85-.90$) and has been shown to correlate with clinical ratings of the severity of depression. In our previous research, CES-D scores have correlated significantly with self-medication smoking and nicotine dependence.

Smoking Urges/Craving (QSU-B)***: The well-validated and reliable 10-item brief Questionnaire of Smoking Urges will assess craving for cigarettes. The QSU-B utilizes a "right now" frame of reference.

Weight Concerns***: Weight concerns associated with quitting smoking will be measured with a reliable ($\alpha=.87$) and valid 6-item scale. Responses to the 6 items range from 1 (not at all) to 10 (very much). Scores are the average of responses to all items.

5.3.2 Mechanisms

Individualized Food (Pre-FCQ-S): In preparation for the food cue-induced craving task, participants will rate how appetizing they find pictures of food (e.g., cupcakes, fruits, vegetables) at the Intake Visit. Foods rated least appetizing (n=20) and foods rated most appetizing (n=20)

CONFIDENTIAL

This material is the property of the University of Pennsylvania. Do not disclose or use except as authorized in writing by the study sponsor

will be selected to create personalized food cue stimuli. This task will be administered during the baseline visit.

Preferred Snack Choice (Pre-RRVF): Participants will select either the salty (Lay's® Classic potato chips) or sweet (M&M's®) snack food as the snack to "work for" when completing the RRVF task over the remainder of the study. This determination will be made at the baseline visit.

Food Cue-Induced Craving (FCQ-S): Food cue-induced craving will be assessed using a personalized food cue exposure paradigm, whereby pictures of foods rated least appetizing (L, n=20), most appetizing (M, n=20), and a picture of a glass of water (W, n=20) will be presented to participants seated at a computer screen. Participants will be instructed to imagine tasting and eating the pictured food for as long as the image is presented. The images will be presented in six blocks. Each block consists of image presentation (10 images, 8 sec duration) and craving assessment. The M, L, and W food cues will be presented in one of two sequences (i.e., MWLMWL or LWMLWM) counterbalanced across participants. Before the task and after each block, participants will complete the state version of the Food Craving Questionnaire, Desire Subscale (FCQ-S). The 3 items (desire to eat, craving, urge to eat) will be tailored to ask about the M, L, and W images on a 5-point scale (strongly disagree to strongly agree). Personalized cues can maximize craving induction and produce greater increases in subjective craving and objective indices of cue reactivity than standard cues. Reactivity to palatable food images is associated with body mass and weight gain. The Food Cue-Induced Craving task will be administered at scan 1 (Day 4), and scan 2 (Day 32) Visits.

Food Reward: Food reward will be assessed by exposing participants to 16 computer-based images of common snack foods spanning caloric content and macronutrient composition (low/high fat sweet, low/high fat savory). After each 5-second snack food exposure, participants will provide ratings of how much they like the food and how pleasant it would be to eat this food right now. Ratings will be made on visual analog scales anchored by 0 (not at all) to 100 (extremely). The food reward task will be administered at baseline.

Food Reinforcement (RRVF): The Relative Reinforcing Value of Food will be assessed via a validated behavioral choice task, permitting the evaluation of the preference for food over other alternatives. Participants will be asked to move a computer mouse to hit targets on one of two sides of a split-screen monitor, to earn points toward either food or money. Participants selected the snack food (salty or sweet) that they wanted to consume for the assessment at the Intake Visit. Using a concurrent schedule, participants will be told that they can switch from working on one side of the screen to the other as often as they wish. Adapted from previous research, participants will be instructed to move the computer mouse to have the cursor hit the targets (either a \$ or food). Consistent with relative reinforcement paradigms, the reinforcement schedule in the money-earning screen will remain constant at a fixed ratio FR-25 (25 targets achieved to earn a point) while the reinforcement schedule for food will increase (require more effort) with a progressive ratio schedule of PR-25x over 10 trials, such that 25, 50, 75, 100, 125, 150, 175, 200, 225, and 250 targets will have to be achieved to earn a point. The computer task will be performed until a participant completes 10 trials and accumulates a total of 10 points from which they will earn either \$0.10 for each point (i.e., up to \$2.00 paid at the end of the task) or a standardized amount (grams) of their chosen snack food for each point. Food earned is consumed at the end of the task to prevent satiation from influencing responding in subsequent trials. Per convention, the RRVF outcome is defined by a breakpoint (maximum amount of responding) for food vs money across the trials. The Relative Reinforcing Value of Food behavioral choice task will be administered at scan 1 (Day 4), and scan 2 (Day 32) visits.

CONFIDENTIAL

This material is the property of the University of Pennsylvania. Do not disclose or use except as authorized in writing by the study sponsor

Positive and Negative Affect (PANAS)***: The Positive and Negative Affect Schedule (1-week frame of reference), a 20-item Likert-format self-report questionnaire, will be used to measure positive mood and negative mood. The two subscales have 10 items each, are internally consistent in both nonpsychiatric and psychiatric samples ($\alpha = .79$ to $.91$), and exhibit good convergent and discriminant validity.

Withdrawal Symptoms (MNWS)***: The Minnesota Nicotine Withdrawal Scale - Revised version (MNWS-R) will measure withdrawal symptoms ($n=15$) associated with quitting smoking. Participants will rate the intensity of their symptoms on the following scale: 0 = none, 1 = slight, 2 = mild, 3 = moderate, 4 = severe and a summary score will be calculated. The MNWS with a 1-week frame of reference will be utilized throughout the trial.

Self-Report Eating Related to Smoking (SWEET)***: The Smoking-Related Eating and Episodes Test assesses 4 content domains related to eating and smoking (Hunger, Craving, Overeating, Body Images) using a 5-point Likert scale (1 = never, 2 = rarely, 3 = sometimes, 4 = often, 5 = always) and how these domains are related to other study measures. The SWEET is collected at the 1 Month Follow-up survey time point to assess smoking to moderate eating, and eating to moderate smoking in a self-report assessment.

Readiness/Intention to Quit Smoking***: Readiness to Quit Smoking will be assessed using the prompt "Please indicate your current thinking about smoking. Responses are on a 9 point Likert Scale (1 = Taking action to quit, 3 = starting to think about how to change my smoking patterns, 5 = I think I should quit but not quite ready, 7 = I think I need to consider quitting someday, 9 = No thought of quitting). Intention to quit smoking will be assessed using the prompt "How likely do you think it is that you will try to quit smoking within the next 30 days?" with responses ranging on a 4 point Likert scale (1 = very unlikely, 4 = very likely). Both of these questions are asked on the 1 Month Follow-up survey only.

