2.2 Overall Objectives - (Recruitment & Retention Pilot Study)

Aim 1: To evaluate the effects of information provision and incentives, alone and in combination, on study enrollment rates.

Hypothesis: Behavioral economic interventions will (Information provision & contingency management) will produce higher rates of enrollment compared to standard recruitment.

3 Study Design

General Design – Main Study

This is a within-subject cross-over neuroimaging investigation of 3 potential neural mechanisms of increased caloric intake during initial smoking cessation. Eighty smokers will be scanned on 2 occasions: (1) after 4 days of monitored abstinence (biochemically verified), and (2) after 4 days of smoking as usual (order counterbalanced) (**Figure 3**). In addition, 30 healthy non-smokers (matched for sex, age, and education) will complete one period of the study to serve as a baseline comparison group (see Exploratory Aim). As in prior studies, participants will have fasted overnight and be provided with a standard meal (BOOST® shake) when they arrive on testing days 4 and 32. Blood oxygen level dependent (BOLD) fMRI sessions will assess BOLD signal at rest and while performing tasks for food cue reactivity, food reinforcement (choice task), and working memory (N-back). Additional measures will be administered out of scanner (**Figure 3**). Caloric intake will be assessed on days 1-3 and 29-31 using a validated dietary recall procedure (days 4 and 32 are fMRI scan days and intake will be standardized). Caloric intake is the primary behavioral outcome. Task-induced BOLD signal change in hypothesized regions of interest and performance on the working memory, food cue, and food reinforcement tasks are the mechanistic variables.

CONFIDENTIAL

This material is the property of the University of Pennsylvania. Do not disclose or use except as authorized in writing by the study sponsor

Figure 3

Non-smoker Control Group (Baseline):

Day	-7	1 2 3 4
Activity	Intake	Period 1*

*non-smokers complete phase 1 with identical monitoring and assessment

**order of periods (abstinence vs smoking) is counter balanced

Smoker Group (within-subject):

Day	-7	1 2 3 4	5-28	29 30 31 32	1 Month Follow-up
Activity	Intake	Period 1	Washout	Period 2	Web-based Survey
State	Smoke	Abstain**	Smoke	Smoke	N/A

Behavioral Outcome:

- Caloric intake (dietary recall; Days 1-3* & Days 29-32)

Intermediate Outcomes: Day 4* & Day 32

- Food reward (out of scanner)
- Working memory (fMRI)

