5.2.7 Washout Period for Smoking Group (~days 5-28)

Between study periods there is a "washout period" (days 5-28) when participants will smoke as usual. No study visits will occur during this time.

5.2.8 fMRI Scan Visits 1 & 2 (~days 4 and 32)

Prior to each scan, participants will be instructed to fast overnight (beginning at ~10pm) until after the completion of their fMRI scanning visit the following day. The fast period will include a Boost® Nutritional Drink (Vanilla) that will be provided during the scanning visit to standardize prior food intake and remove deprivation to increase sensitivity to changes in food reward. Since participants are asked to fast overnight, all scanning sessions will be scheduled to occur in the morning. However, a scan may be completed in the afternoon at the discretion of the Principal Investigator due to extenuating circumstances. Additionally, participants will be instructed not to consume caffeine for 4 hours prior to the beginning of the visit in order standardize satiety. Including the 1-hour fMRI scan, scanning visits are expected to last ~4 hours in duration. If a scanner hardware/software malfunction occurs and data is unable to be collected, an fMRI scan(s) may be rescheduled at the discretion of the Principal Investigator.

CONFIDENTIAL

This material is the property of the University of Pennsylvania. Do not disclose or use except as authorized in writing by the study sponsor

At both scanning visits participants will:

1. Complete a urine drug screen (at least 30ml [two tablespoons] of urine). The urine drug screen will assess the use of any study-prohibited medications/recreational drugs (See Key Exclusionary Criteria; Alcohol/Drugs). Participants who test positive for any study-prohibited medications/recreational drugs will be deemed ineligible for the study at the discretion of the Principal Investigator.
2. Self-administer a CLIA-waived urine pregnancy test (female participants only). Participants who believe that they may be pregnant are instructed to discontinue participation in the study at this time.
3. Perform a BrAC assessment to control for alcohol consumption.
 - Participants with a BrAC greater than 0.000 will be ineligible to complete the study unless the Principal Investigator permits the participant to reschedule the neuroimaging scan to another day.
4. Perform a CO breath assessment

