5. Self-report smoking behavior over the past 24 hours to control for prior tobacco exposure and provide their daily smoking rate (timeline follow back [TLFB]) (smokers only).
6. Have weight measured.
7. Complete a magnet safety form***.
8. Complete paper and pencil questionnaires (craving, withdrawal, mood, eating)***.
9. Complete a set of abbreviated practice tasks similar to those that will be administered during the fMRI scan. Participants will be expected to demonstrate an understanding of the tasks and the response device prior to the fMRI scan.
10. Be provided with a Boost® Nutritional Drink and water.
11. Be escorted to the imaging facility at either the Hospital of the University of Pennsylvania or the Stellar Chance building for the brain-scanning portion of the session.
12. **SMOKING SCAN ONLY:** Participants will smoke one of their own cigarettes (~45 min. before initiating fMRI) in a designated smoking area outside of the building where the fMRI scanner is located in order to standardize the timing of cigarette exposure for all participants.
13. Undergo a 1-hour fMRI scan adhering to the procedures and Table 1 below:

Scanning Protocol/Data Acquisition: MRI is performed in a 1-hour session, which, in our experience, participants tolerate easily without discomfort or excessive motion. Prior to entering the scanning area, an approved MRI Technician or MRI User will review the participant's magnet safety form and will confirm that the participant has removed all metal and/or objects containing magnetic strips from their persons. Once the participant is approved to enter the scanning area, the participant will be placed supine in the scanner, wearing earplugs to muffle noise, and fitted with adjustable foam cushions to limit head motion. If a participant requires corrective lenses for vision, but does not have contact lenses, a set of plastic glasses that are approved for use in an MRI scanner will be provided to him/her. Participants will be provided with an emergency squeeze ball, so that they may interrupt the scan and/or be removed from the scanner if necessary. Head fixation will be assured through a foam-rubber device mounted on the headcoil.

CONFIDENTIAL

This material is the property of the University of Pennsylvania. Do not disclose or use except as authorized in writing by the study sponsor

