Aim 2 seeks to determine the additional explanatory value of brain signal over and above models using only clinical, subjective, and behavioral performance measures (**H2a**). The use of difference scores reduces a complex longitudinal analysis of mediation to an analysis of a single (non-repeated) measure. Our analyses will test for incremental change in R^2 when models incorporate brain data. We will also examine the correlations among our predictors and identify potential for collinearity via variance inflation. We will then construct models of $\Delta kCal$ admitting blocks of variables hierarchically, and testing for improvement in fit by Wald test, starting with clinical variables (age, sex, FTND, BMI), behavioral performance, and subjective responses to abstinence challenge (N-back, MNWS, QSU-B, food reinforcement task breakpoint). Finally, we will add the difference scores from imaging, and estimate overall improvement (**H2a**) in R^2 . At each stage, we will allow highly redundant variables to drop out if variance inflation factor (VIF) is greater than 5. We will then return to the clinical plus behavior model and test the addition of each brain domain separately, again using the incremental improvement in R^2 by domain (**H2b**). Finally, we will explore data reduction methods (Principle Component Regression, Partial Least Squares) for entering correlated imaging variables in order to minimize the confounding effects of correlated predictors.

Our Exploratory Aim is a between-group analysis to provide a baseline comparison in food-related brain response between smokers and non-smokers. The analysis will include 30 non-smokers who will take part in a single non-smoking phase of the study and will include each of the predictor measures in H1. The analysis will utilize one-way ANOVA methods, fitted with GEE regression (Gaussian family), with a 3-level design code representing non-smoker, smoker sated, and smoker abstaining (non-smokers will have only one entry per subject, smokers will have two). Non-smokers will be treated as the reference group. Comparisons of interest, non-smoker versus sated smoker, and non-smoker versus abstaining smoker, will be tested using the z-score corresponding to the regression coefficient. A small number of covariates may be included in the model to control error.

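### The withdrawal scale (MNWS) looks back one week inside 4-day periods, which mixes smoking days into an abstinence score that brain signal must beat in H2a

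*Combined protocol and SAP*

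**What the plan says.** Section 5.3.2 (Mechanisms) sets the recall window of the withdrawal scale: "The MNWS with a 1-week frame of reference will be utilized throughout the trial". The mood scale has the same window: "The Positive and Negative Affect Schedule (1-week frame of reference), a 20-item Likert-format self-report questionnaire". Section 5.3.1 gives the craving scale, QSU-B, a present-moment frame.

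Section 3 (General Design – Main Study) sets each period at 4 days, with scans on days 4 and 32 and caloric intake recorded for days 1-3 and 29-31. Section 5.2.7 has smokers smoking as usual, with no visits, on days 5-28.

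Section 5.6 analyses Aim 2 on difference scores. Clinical, behavioural and subjective variables enter first, among them "subjective responses to abstinence challenge (N-back, MNWS, QSU-B, food reinforcement task breakpoint". Imaging differences enter last, and H2a rests on the rise in R². The section does not say which day's MNWS, or what average, forms the difference. PANAS is not in the list.

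On timing, the scan-visit section (5.2.8, fMRI Scan Visits 1 & 2) includes this step for both visits: "Complete paper and pencil questionnaires (craving, withdrawal, mood, eating". In Table 2, as extracted, the MNWS and PANAS rows are ticked on days 1-3 and 29-32 but blank on day 4. The QSU-B row is ticked on day 4.

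**The concern.** The recall window is longer than the state it is meant to measure. During abstinence, a past-week question asks about a mixture of abstinent and smoking days, and a difference score built on it is diluted.

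This matters because H2a is a contest. It claims that brain signal describes the abstinence-induced change in intake better than clinical, subjective and behavioural measures alone, and withdrawal is one of the two subjective measures it names. If withdrawal is measured poorly and brain signal is correlated with withdrawal, the brain variables can pick up variance that belongs to withdrawal. H2a could then be declared without brain signal adding anything of its own.

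The unspecified scoring day and the day-4 gap in Table 2 add to this, because the dilution depends strongly on which day is used.

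**Working it through.** **1. The plan's own figure.** The documents give no power for the H2a increment and no figure for the recall window. The nearest is Aim 2b in section 5.5: effect size about 0.5, p<0.01 two-sided, 96% power. With 80 smokers, Φ(0.5×√80 − 2.576) = Φ(1.896) = 97.1%; the noncentral t gives 96.4%. The stated figure reproduces and is not disputed. With N=110 the t result is 99.5%, so the calculation rests on the 80 smokers, and N=80 is used below.

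**2. Day count.** For a 7-day window ending on day k of abstinence, the abstinent share f is k/7 if the day of rating counts and (k−1)/7 if it does not.

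| Abstinence day | f, today counted | Smoking share | f, today not counted | Smoking share |
|---|---|---|---|---|
| 1 | 1/7 = 14% | 86% | 0% | 100% |
| 2 | 2/7 = 29% | 71% | 1/7 = 14% | 86% |
| 3 | 3/7 = 43% | 57% | 2/7 = 29% | 71% |
| 4 | 4/7 = 57% | 43% | 3/7 = 43% | 57% |

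**3. Which side is diluted.** For participants who abstain first, a window ending on day 29 reaches back to day 23 (today counted) or day 22, inside the days 5-28 washout. The smoking-period score is therefore clean, and only the abstinent side is diluted. If recall weights days equally, the mean difference shrinks to f of its true size.

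**4. Effect on H2a (illustration).** Write the MNWS difference as M = fW + (1−f)P + E. W is the true withdrawal change (variance 1), P the difference between the two pre-period smoking spells (variance v), and E rating error (variance e). Then

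corr(M,W) = f / √(f² + (1−f)²v + e).

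If v = e = 0 this is 1 for any f above 0. Pure shrinkage leaves R² unchanged, and the false-positive rate stays at 5%.

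Otherwise, take one brain predictor B with no effect on kcal (Y) beyond W. With r(MY) = r(WY)·corr(M,W), r(MB) = r(WB)·corr(M,W) and r(BY) = r(WY)·r(WB):

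R² = [r(MY)² + r(BY)² − 2·r(MY)·r(BY)·r(MB)] / [1 − r(MB)²], ΔR² = R² − r(MY)², noncentrality = 80·ΔR²/(1−R²), tested on F(1,77) at 0.05.

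The documents give none of the inputs. The assumptions are:
- Model A: v = 0.25 to 1, e = 0, r(WY) = 0.4.
- Model B: v = 0, e = 0.3/0.7 (reliability 0.70 with a period-confined frame), r(WY) = 0.3/√0.7 = 0.359, so that the period-confined score explains 9% of the kcal change.

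Chance of declaring a brain improvement that is not there:

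| f | A, r(WB)=0.4 | A, r(WB)=0.6 | B, r(WB)=0.4 | B, r(WB)=0.6 |
|---|---|---|---|---|
| 1 (period-confined) | 5% | 5% | 7% | 11% |
| 4/7 | 5.5-8.8% | 6.3-15% | 12% | 23% |
| 3/7 | 7.8-16% | 13-33% | 15% | 31% |
| 2/7 | 15-24% | 31-49% | 20% | 39% |
| 1/7 | 26-29% | 52-57% | 23% | 47% |

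Example (A, v = 0.25, f = 4/7, both correlations 0.4): corr(M,W) = 0.571/√(0.3265+0.0459) = 0.936, r(MY)² = 0.140, ΔR² = 0.0005, rejection 5.5%. QSU-B and the other predictors are left out of this illustration.

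**5. Table 2 against the text.** If Table 2 is followed, there is no day-4 score to set against day 32, and the matched days are 1-3 against 29-31, where smoking days dominate. If instead the last score of each period were used (day 3 and day 32), the abstinent share would be 3/7 for those who abstain first and 4/7 for those who abstain second (today counted), so it would depend on the assigned order.

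**The case against.** The strongest defence is that the effect is limited and conditional. Only one predictor in a larger block is affected, since QSU-B already asks about the present moment. Shrinkage alone costs no R². On day 4 with today counted, model A puts the false-positive rate at 5.5-8.8% with the weaker brain correlation. The scan-visit text does call for withdrawal ratings at both scans. All of this stands, and it limits the point. It does not remove it: a summed self-report has some rating error, the scoring day is open, and the less favourable days are not ruled out.

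Several stronger readings are tempting but not supported:
- A reader might infer that the abstinence score is always mostly smoking days. That holds on days 1-3. On day 4 it fails if the day of rating counts (3 of 7).
- A reader might infer that PANAS also tilts H2a. It is not in the section 5.6 block, so its 1-week frame is a measurement problem only.
- A reader might infer that H2a is shown to be biased, or that MNWS loses a known share of explained variance. Under model B, its R² would fall from 9% to 0.6%, 2.1%, 3.9% or 5.6% on days 1-4, but only because rating error is held at full size. If error shrank in proportion, it would stay at 9%.
- A reader might infer that Table 2 leaves no usable difference score. Days 1-3 against 29-31 remain, and they match the dietary recall days.
- Overlap between consecutive daily windows might look like a further fault. It is not one here, because Aim 2 uses a single difference score.

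**Conclusion.** The point holds in a limited form. A 1-week MNWS frame within 4-day periods fills 57-100% of the window with pre-period smoking days on days 1-3 and 43-57% on day 4. This follows from the calendar alone.

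A weaker H2a comparator, and so an easier brain increment, is the probable direction. It rests on rating error or pre-period variation, and on brain signal correlated with withdrawal. The percentages in the second table illustrate that direction under assumed inputs and do not estimate this trial's error rate. The day-4 conflict between Table 2 and the scan-visit text is real as extracted, though a fault in reading the table from PDF cannot be excluded. This is a cheap improvement, not a threat to the trial as a whole.

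**What to change.** 1. On days 1-4 and 29-32, give MNWS (and PANAS if it is analysed) with a frame confined to the period: 'today' or 'right now', or the past 24 hours from day 2 or 30 onward. Do not use 'since the last visit'. With no visits in the washout, on day 29 it would reach back to day 4, an abstinent day for those who abstained first, and on day 1 to the baseline visit on day -7.
2. Reconcile Table 2 with the scan-visit section so that both scales are collected on day 4 as well as day 32.
3. In section 5.6, name matched days for the H2a MNWS difference (for example day 4 against day 32), the same for both orders.
4. Keep one frame within each participant. Anyone who has started period 1 on the 1-week frame finishes on it. Add a frame indicator for them, and report H2a with and without these participants or MNWS.

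The cost is a questionnaire wording amendment, a table edit and one sentence in the analysis plan. The downside is two recall frames in the dataset. Section 5.2.10 records 15 completers as of 14 April 2020, against a target of 80 smokers; the documents give no later count. If collection is already complete, item 3 and a report of H2a with and without MNWS can still be done.
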